METHODOLOGY

This is a longitudinal observational cohort study of individuals, seeking to define the immunological memory immune response following SARS-CoV-2 infection. Sequential observations and clinical samples will be taken from individuals who have had SARS-CoV-2 infection as determined by positive antibody response, regardless of disease severity and as determined by symptoms, government testing or antibody testing as part of ALSPAC. Individuals who have not had infection with SARS-CoV-2 will be recruited as controls, and these participants will undergo the same sequential observations and clinical sampling procedures. The samples obtained from this protocol will then be analysed to examine the immune response to SARS-CoV-2, to determine whether robust long-lived immunological memory to SARS-CoV-2 is established, how long it persists after recovery from COVID-19 and how this is influenced by a range of different factors and clinical phenotype.

This study will use the Avon Longitudinal Study of Parents and Children (ALSPAC – also known as Children of the 90s by participants and the public) to recruit participants. Between April 1991 and December 1992 ALSPAC recruited more than 14,000 pregnant women into the study and these women (some of whom had two pregnancies or multiple births during the recruitment period), the children arising from the pregnancy, and their partners have been followed up intensively over two decades and we hold detailed historical data and biological samples for these participants with consent for use in future research. The original study mothers and their partners are referred to as the G0 cohort. The original offspring and now their partners are referred to as the G1 cohort.

Participant Selection

ALSPAC have undertaken 5200 serological SARS-CoV-2 tests on G0 and G1 cohort participants and administered questionnaires to participants during the pandemic. In order to achieve the research objectives outlined in this protocol, in each clinic round this study will aim to recruit:

- All G1 individuals and a comparator sample of G0 individuals meeting eligibility criteria who meet the study definition of cases
- Up to 200 G1and G0 individuals meeting eligibility criteria who meet the study definition of controls

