Information from these along with linked NHS medical records data will be used to identify potential participants. Based on seroprevalence estimates, ALSPAC cohort size, and estimations of typical response to similar studies, this study therefore estimates recruiting approximately:

- 100 cases of previous SARS-CoV-2 infection at Visit 1 (approx. upper limit of 250 cases)
- 100 control individuals without previous SARS-CoV-2 infection age, sex and symptom matched to cases and 100 random controls without previous SARS-CoV-2 infection (approx. upper limit of 250 controls)

Where needed (i.e. if there are large numbers of potential cases), priority will be given to participants with pre-pandemic measures of BMI and lung function (objectively assessed at the age of 24 years) and previous biological samples.

[figure not shown]
As part of an initial visit, blood will be taken and the antibody and T-cell response to SARS-CoV-2 determined. Individuals who are cases with a SARS-CoV-2 antibody response and/or a positivie T-cell response will be enrolled in the SARS-CoV-2 arm. Individuals who are cases with information available that there is no detectable SARS-CoV-2 antibody or T-Cell response will be considered seronegative and will not be required to participate further in the study. Individuals who are recruited as controls and have a confirmed SARS-CoV-2 antibody negative response will be enrolled into the control arm for two remaining visits, sufficient negative controls will be recruited to allow for the possibility that some controls will become infected with SARS-CoV-2 during the duration of the study and will not be eligible to complete all four visits. Those who were initially recruited as controls

who have subsequently tested positive will also be retained in the study and will move from control arm to case arm as appropriate. Where cases are no longer available, but new cases are defined, sample size will be maintained by the recruitment of new case events.

Pilot study

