- (9) Assess prevalence of cross-reactivity against circulating CoVs and how this might influence the outcome of response to COVID infection.
- (10) Assess changes in the exercise capacity test, SF36 and self-reported dyspnoea during the convalescent period.

Study design

This is a longitudinal observational cohort study of adults within the Bristol area, conducted on individuals who may fall into the following groups of patients:

- (1) healthy seronegative controls (some of whom may become infected during the study),
- (2) asymptomatic/pauci-symptomatic
- (3) symptomatic infection not requiring hospitalisation,
- (4) moderate illness not requiring hospitalisation,
- (5) hospitalised patients who did or did not require mechanical ventilation

Sampling framework

Current estimates of COVID-19 prevalence in the SW England (based on seroprevalence data) range between 2-6%, with age and time since infection contributing to differences in patient groups. It is therefore reasonable to assume that seroprevalence is approximately 3%. ALSPAC have undertaken 5000 serological SARS-CoV-2 tests on cohort participants; therefore, if only 3500 of these are returned, we would expect to identify 100 individuals seropositive to SARS-CoV-2. If only 50% of these 100 individuals wish to enter into this study, the cohort of seropositive individuals would be 50.

The number of seropositive individuals will be increased by incorporating ALSPAC cohort individuals who:

- 1. self-report as being highly likely to have had COVID-19 infection (from either positive SARS-CoV-2 PCR test performed at NHS care facility, COVID-19 testing site or home testing), **OR**
- 2. have been told by a physician that, in the opinion of that doctor, they have had a clinical illness likely to be COVID-19 **OR**
- 3. based on a combination of symptoms they are likely to have been cases

DATA COLLECTION

Cases - inclusion criteria

This study will be undertaken on participants of the ALSPAC cohort meeting the following criteria:

- 1. Aged 25 or over, AND
- 2. Individuals who have undergone SARS-CoV-2 antibody testing through the ALSPAC SARS-CoV-2 serology study (IRAS 289493), **OR**
- 3. Individuals who self-report or through linkage to official health records as being highly likely to have had COVID-19 infection (from either positive SARS-CoV-2 PCR test performed at NHS care facility, COVID-19 testing site or home testing), **OR**

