- 4. Individuals who have been told by a physician that, in the opinion of that doctor, they have had a clinical illness likely to be COVID-19.

Control participants – inclusion criteria

- 1. Aged 25 or over, AND
- 2. Individuals who self-report as not experiencing symptoms of COVID-19 via the symptom survey and do not have case status through linkage to official health records, **AND**
- 3. Self-report as not having had positive SARS-CoV-2 molecular test, AND
- 4. Are confirmed SARS-CoV-2 seronegative at Visit 1 and then at visit 2

Exclusion criteria for both controls and cases

- 1. Do not wish to participate in this research study
- 2. Participants taking blood thinners (e.g. warfarin) or with a known clotting disorder
- 3. Do not meet eligibility criteria for respective arm

Invite procedure

An initial invitation email (*Initial invite v2*), and link to a participant information sheet (*Information Sheet v2*) will be sent to eligible participants, via contact details held, with participant consent, in the ALSPAC contact management system. Appointments will be offered on a range of days and times, including weekends. Participants will be able to respond by telephone or email. A reminder email will be sent if there is no response after one weeks (*Reminder email v2*) and if they do not respond after a further week they will be called by a member of the ALSPAC research team. This is an invitation procedure used previously within ALSPAC and study participants are familiar with contacts from the study by these methods.

Following the initial visit, samples will be analysed for current serological response. Those cases who are seropositive or T-Cell positive at Visit 1 and all controls whether confirmed as seronegative or seropositive will be invited (*follow up invite v2*) to complete repeat visits 4 months, and 8-12 months post visit 1. Those not eligible to continue the study will be notified by email (*follow up no visits v2*).

Where cases are no longer available, but new cases are defined, sample size will be maintained by the recruitment of new case events.

Before the clinic visit - (Visits 1-4)

Once booked for an appointment, the participant will be sent a confirmation email (*Confirmation letter v1, with a link to visiting children of the 90s COVID-19 information sheet*) and then an appointment reminder call the day prior to their appointment this will include a check for any current COVID-19 symptoms.

At the clinic visit

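### The protocol plans 100 symptom-matched controls, but its control criteria admit only people who report no COVID-19 symptoms, so symptomatic cases have no eligible symptom match

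*Protocol*

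**What the plan says.** Participant Selection expects about 100 cases at Visit 1, with an approximate upper limit of 250. Alongside them it plans "100 control individuals without previous SARS-CoV-2 infection age, sex and symptom matched to cases and 100 random controls without previous SARS-CoV-2 infection". The same section limits control recruitment in each clinic round to "individuals meeting eligibility criteria who meet the study definition of controls".

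The section Control participants – inclusion criteria gives one list for all controls, joined by AND. Criterion 2 reads, in part, "Individuals who self-report as not experiencing symptoms of COVID-19 via the symptom survey and do not have case status through linkage". The other criteria are age, no self-reported positive molecular test, and seronegativity at Visits 1 and 2. The exclusion criteria for both arms add "Do not meet eligibility criteria for respective arm".

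Study design lists one group of healthy seronegative controls and four groups of infected participants. The infected groups run from "asymptomatic/pauci-symptomatic" through "symptomatic infection not requiring hospitalisation" and moderate illness to hospitalised patients.

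**The concern.** A symptom-matched control for a symptomatic case is someone without SARS-CoV-2 infection who had similar symptoms. Criterion 2 bars that person from the control arm. Staff selecting controls therefore have two instructions that cannot both be followed for a symptomatic case.

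The comparison between cases and controls is at stake. Controls undergo the same visits and sampling as cases, immune profiling covers both, and Descriptive analysis of other measures contemplates comparing the arms on key outcomes. If every control is free of COVID-19 symptoms, a difference between the arms may reflect SARS-CoV-2 infection, having had a symptomatic illness, or both. Analysis cannot separate the two afterwards, because the controls needed to do so were never enrolled.

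**Working it through.** No sample-size formula applies: the 100 matched controls are a recruitment estimate with no power calculation behind them. The check sets the sections side by side.

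1. **Matching rule (Participant Selection).** 100 controls are matched on age, sex and symptoms. The symptoms and their time window are not defined.
2. **Eligibility (control inclusion criteria).** Criterion 2 requires no self-reported COVID-19 symptoms. It is joined to the others by AND, and no separate list exists for the matched set.
3. **Enforcement.** Recruited controls must meet the eligibility criteria and the control definition, and failing the criteria of one's arm is an exclusion.
4. **Other sources of symptomatic controls.** There are none. Suspected cases with no antibody or T-cell response leave the study after Visit 1 and are not moved to the control arm. Study design lists no symptomatic control group.
5. **Who is affected.** Any case who had COVID-19 symptoms, including the pauci-symptomatic part of the mildest group. Fully asymptomatic cases can still be matched.

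**Size.** Let N be the number of cases and f the share without COVID-19 symptoms. At most N × f cases can have an eligible symptom match, and N × (1 − f) cannot. N = 100 comes from Participant Selection; f is not given, so a range is assumed:

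| Assumed f | Matchable, 100 × f | Not matchable, 100 × (1 − f) |
|---|---|---|
| 10% | 10 | 90 |
| 20% | 20 | 80 |
| 40% | 40 | 60 |
| 50% | 50 | 50 |

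All 100 can be matched only if f = 100%. At the upper limit of 250 cases, the 100 matched places could all be filled if f were at least 100/250 = 40%, but only against symptom-free cases. Symptomatic cases would still have no match.

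The Sampling framework gives some reason to doubt that f is close to 100%. It allows for only 50 participants from the serology route if half agree, leaving 100 − 50 = 50 of the target from elsewhere. Two of the three added routes are a physician's opinion of a likely COVID-19 illness and a combination of symptoms. This does not fix f.

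**The case against.** The strongest defence is the wording of criterion 2. It is in the present tense, is specific to COVID-19 and gives no time window, and symptom questions had been put to the cohort on three earlier occasions. If the criterion means symptoms current at one survey, matching on past or more general symptoms might be possible. This stands as a reason to ask for a definition, but it does not remove the conflict. The text does not adopt that reading, and the criterion sits beside the absence of case status and of a positive molecular test, where it works as a screen against past infection. The flow diagram could not be read here, and its footnote only refers back to the control screening criteria.

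A second defence is that little depends on the matching. The primary objective is mainly description within cases, and the case-control comparison is conditional on how many controls enrol. That limits the consequence to the contrasts between arms.

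A reader might also infer more than the documents support:

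- **That the random controls are not random.** Random can mean drawn at random from eligible people, in contrast to matched. Study design calls controls healthy, so symptom-free random controls may be intended.
- **That differences between arms are inflated.** The mixing of effects follows from the text. Its direction and size do not.
- **That the matched set was meant to isolate SARS-CoV-2 from similar illnesses.** The protocol states no purpose for it.
- **That three of the four infected groups being clearly symptomatic gives the share affected.** The group sizes are not stated.

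**Conclusion.** The protocol is wrong as written on this point: symptom matching and control criterion 2 cannot both be applied to a case who had COVID-19 symptoms. For those cases the matched set is matched on age and sex only, and on COVID-19 symptoms it resembles the random set. Case-control contrasts then carry the effect of symptomatic illness along with that of infection.

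The number of cases affected is 100 × (1 − f), with f not given; the 50 to 90 shown is an illustration. The conclusion assumes that symptoms in the matching statement means COVID-19 symptoms, and that criterion 2 covers the period of the possible infection. It does not extend to fully asymptomatic cases or to the within-case description of immune memory.

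**What to change.** Reconcile Participant Selection with the control inclusion criteria in one of two ways.

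**If symptom matching is wanted,** give the matched set its own criterion: no positive SARS-CoV-2 test, no linked case status, and both antibody and T-cell results negative at Visit 1. Use symptoms as the matching variable, with a list and time window taken from the existing survey, and not as an exclusion. Keep criterion 2 for the random controls and describe them as random among symptom-free seronegative people. The T-cell condition is needed because control enrolment now rests on antibody status alone, while a T-cell response is enough to keep a suspected case in the case arm.

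**If symptomatic controls are not wanted,** delete symptoms from the matching statement and do not describe the set as symptom matched.

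Either way the cost is a protocol amendment, which needs sponsor and ethics review before use. The first option also carries a small added risk of undetected past infection among symptomatic controls. It needs no new assay, since Visit 1 already determines both responses, but matched status can be confirmed only once those results are in. It would also remove uninfected people with cross-reactive T cells from the matched set, so the cross-reactivity objective should not rely on that set.

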It remains unclear as to whether long-lived robust immunological memory is formed after infection with SARS-CoV-2. As a novel human pathogen, there is little data to indicate how long immune memory persists for and in what proportion of patients it occurs. Following recovery from infection with many viruses, robust long-lived immunological memory responses occur and prevent re-infection from that virus. However, infection with some viruses does not stimulate sustained immunological memory and therefore it is possible to be re-infected with the same virus. Data

Protocol v2.0 02/02/2021

suggests that immunological memory formed following infection with other human coronaviruses may not be long lived. However, to date, there has been no study conducted to determine the magnitude, quality, and persistence of immune memory after SARS-CoV-2 infection.

The duration of immunity is critical to make informed decisions regarding the easing of public health control measures. For example, if immunity to COVID-19 is short-lived, there may therefore be increasing number of cases over the winter, which would help inform key decisions to refine and adapt the UK's public health control measures and ensure their feasibility for a prolonged period. In addition, we will generate data that is relevant to the development and implementation of vaccine programs.

It is also essential to establish how factors such as age, co-morbidity, disease severity, the occurrence of hyperinflammation (e.g. Kawasaki-like disease) and persistent immune activation influence the degree of immunological memory established. It is crucial that these key questions are answered because this will enable:]

- (1) accurate modelling of global SARS-CoV-2 transmission dynamics and the impact of non-pharmaceutical interventions,
- (2) development of vaccines capable of stimulating protective immunity; and,
- (3) optimal design of vaccine strategies (if/when vaccines become available) to achieve protection that is sustained, as it may or may not be necessary to vaccinate individuals who have previously been infected with SARS-CoV-2.

This work will define the duration, nature and efficacy of the immune response following SARS-CoV-2 infection. It is critical as it will help understand the immunological responses in individuals following SARS-CoV-2 infection by undertaking a longitudinal observational cohort study of participants and define the immunological memory response following SARS-CoV-2 infection.

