A pilot study will be undertaken on up to 10 healthy volunteers, who will be recruited on the basis that they are willing to participate in the pilot and have neither a clotting disorder nor are taking any blood thinning medication. These individuals will be asked to undergo the procedures outlined in this protocol including infection control measures, informed consent, blood sampling (4x10ml EDTA, 1x5ml Serum), saliva sample, physical measures, respiratory function testing, urine sample and a questionnaire. The pilot will be undertaken in order to ensure that operational and research standards are sufficiently operational before commencing the finalised study.

Study Flow Diagram

- · Control participants met control screening eligibility criteria
- † SARS-CoV-2 participants met study eligibility criteria

Primary Objective

To determine and describe SARS-CoV-2 specific humoral and cellular responses longitudinally and determine the magnitude and duration of immunological memory following COVID-19 infection.

Secondary Objectives

The secondary outcomes are:

- (1) To determine and describe the nature, specificity and long-term persistence of the SARS-CoV-2 specific antibody response
- (2) To determine how the SARS-CoV-2 specific antibody response relates to clinical phenotype
- (3) To determine and describe the nature, specificity and kinetics of the B-cell memory response following COVID-19 infection, and in relation to clinical phenotype
- (4) To identify key B-cell and T-cell epitopes to enable functional analysis of the SARS-CoV-2 memory response, and inform vaccine design
- (5) To determine the magnitude, breadth, functional phenotype, and persistence of the T-cell response
- (6) To describe how the memory T-cell response to SARS-CoV-2 relates to clinical phenotype of COVID-19 infection
- (7) To describe and determine the effect of SARS-CoV-2 infection on components of the innate immune system, including:
 - a. inflammation-related serum proteins (e.g., complement, C-reactive protein, lectins such as mannose-binding lectin, and ficolins).
 - b. phagocytes and cells that release cytokines and inflammatory mediators.
 - c. surface and phagocyte granule antimicrobial peptides.
 - d. cell receptors that sense microorganisms and signal a defensive response (e.g., Toll-like receptors); and,
- (8) To determine and describe the impact of hyperinflammation and chronic immune activation on the generation of long-term immunity

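### The Visit 1 retention rule also drops laboratory-confirmed cases who show no response, so persistence in the followed arm is conditional on having memory at entry

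*Protocol*

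**What the plan says.** Participant Selection (Methodology) tests both antibody and T-cell response at the first visit. It then states that "cases with a SARS-CoV-2 antibody response and/or a positivie T-cell response will be enrolled in the SARS-CoV-2 arm", while cases with "no detectable SARS-CoV-2 antibody or T-Cell response will be considered seronegative and will not be required to participate further in the study". Read together, the two sentences mean that one positive response is enough to stay and that a case leaves only when both are absent.

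The Invite procedure (Data Collection) repeats the rule for follow-up: "Those cases who are seropositive or T-Cell positive at Visit 1 and all controls whether confirmed as seronegative or seropositive will be invited" to visits at 4 months and at 8-12 months after Visit 1. Those not eligible to continue are told so by email, so the rule is not an optional exit.

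The case inclusion criteria do not depend on the Visit 1 result. They admit people through the earlier ALSPAC serology study, through a "positive SARS-CoV-2 PCR test performed at NHS care facility" (or at a testing site or at home, by self-report or record linkage), and through a physician's opinion. The Sampling framework adds likely cases by symptoms.

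The Primary Objective is to "determine the magnitude and duration of immunological memory following COVID-19 infection". The Methodology section adds the aim "to determine whether robust long-lived immunological memory to SARS-CoV-2 is established, how long it persists after recovery from COVID-19". The Rationale notes, as background, that little is known about "how long immune memory persists for and in what proportion of patients it occurs".

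**The concern.** Continued follow-up as a case depends on the quantity under study. A person with a positive PCR who has neither response at Visit 1 either never mounted a detectable response or lost it before the visit. A person with an earlier positive serology result who has neither response has apparently lost an antibody response between two dated tests. Both bear directly on whether memory is established and how long it lasts. The rule relabels such people as seronegative and ends their participation, and the protocol nowhere limits its conclusions to Visit 1 responders.

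Participants are recruited at different times after infection, so someone seen late has had longer to lose a response and is filtered more heavily than someone seen early. The objectives that relate memory to clinical phenotype or hyperinflammation would also lose the weakest responders. The Rationale intends the results for transmission modelling and vaccine strategy, and both would inherit an optimistic estimate.

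**Working it through.** **No plan figure to reproduce.** The protocol states no response rate, waning rate or precision for this objective. Everything numerical below is an assumption that shows direction and rough size.

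**Step 1: identity.** Let p be the share of truly infected cases with at least one response at Visit 1, and q the share of those still positive at the last visit. If lost responses do not return:

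- followed arm: 100% at Visit 1, then q
- all infected: p at Visit 1, then p × q
- ratio of followed arm to all infected: 1/p

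For p = 0.95, 0.90, 0.80 and 0.70 the ratio is 1.05, 1.11, 1.25 and 1.43. The direction is certain whenever p is below 1. The size depends wholly on p, which the documents do not give.

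**Step 2: a model of the actual rule.** A case leaves only if both responses are absent, so the model needs two markers. Assumptions:

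- each marker's log2 level above the detection threshold at month 1 is normal with SD 1.5 and mean 4 (scenario A) or 3 (scenario B)
- half-life is log-normal with median 4 months and log-SD 0.5
- Visit 1 is uniform on 2-10 months after infection, and the last visit is 10 months later
- a marker is detectable while its starting level minus (t − 1)/half-life exceeds 0
- the two markers have the same distribution, with correlation 0 or 0.5 in both level and half-life

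| | A, corr. 0 | A, corr. 0.5 | B, corr. 0 | B, corr. 0.5 |
|---|---|---|---|---|
| Cases dropped | 1.1% | 2.8% | 4.5% | 8.4% |
| Overstatement, antibody positivity at last visit (points) | 0.6 | 1.5 | 1.6 | 3.2 |
| Overstatement, any response at last visit (points) | 0.8 | 2.0 | 2.7 | 4.6 |
| Median half-life among retained (true 4.0 months) | 4.02 | 4.06 | 4.06 | 4.13 |

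The identity checks the table. In B with correlation 0.5, any response at the last visit is 50.2% in all infected, and 50.2% / (1 − 0.084) = 54.8%, the value in the retained group.

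**Step 3: time since infection.** Across the same four settings, 0-1.5% of cases are dropped when Visit 1 falls at 2-4 months, against 3-18% when it falls at 8-10 months. Selection is concentrated in late entrants.

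**Step 4: why one marker is not enough.** If a case left on losing a single marker, the same assumptions would drop 8% (A) or 18% (B) and overstate antibody positivity by 4.5 or about 7.8 points. That rule is stricter than the protocol's, so those figures overstate the effect.

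**Scale.** With the planned 100 or so cases at Visit 1, 1-8% is about 1 to 8 people.

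**The case against.** **The rule confirms infection.** This stands for part of the cohort. Cases may enter on a physician's opinion or on symptoms, and the serology criterion requires only having been tested, not a positive result. Some people negative on both responses were never infected, and keeping everyone would bias the other way: if 90% of infected people respond but only 70% of enrolled cases were infected, the apparent response at Visit 1 is 0.9 × 0.7 = 63%. A reader might infer that every released case is a lost non-responder. The entry routes do not support that. The point holds only for people with laboratory evidence before Visit 1.

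**The data are not discarded.** This also stands. The rule ends participation, and nothing says that Visit 1 results are deleted. An analysis can still count them, and the statistical analysis plan, which is not at hand, may do so. But the protocol places these people outside the SARS-CoV-2 arm, and no analysis can recover later samples that were not taken, including any late or returning response.

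**The target may be the course of memory in responders.** Partly fair. The proportion wording is background in the Rationale, not a listed objective, and the Methodology describes "individuals who have had SARS-CoV-2 infection as determined by positive antibody response". A reader might infer that a stated proportion endpoint is invalidated; no such endpoint exists. However, the Methodology does ask whether memory is established, and no passage restricts conclusions to responders.

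**Mitigation.** Controls who become infected move to the case arm and do not pass through the case filter at Visit 1. This helps, but only for incident cases.

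**Conclusion.** The concern holds for cases with a positive PCR or positive serology before Visit 1. Their release makes establishment and persistence in the followed SARS-CoV-2 arm conditional on a response at entry and biased upward, increasingly so with later entry.

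The size cannot be derived from the documents. Under the two-marker assumptions above, about 1-8% of cases are dropped, final positivity is overstated by about 0.5-5 points, and median half-life barely moves. A reader might infer a much larger distortion, for example 8-24 points by assuming that 10-30% of confirmed cases are negative at Visit 1 and that 80% of the rest persist (80% against 72% to 56%). The protocol supports neither input. A markedly flattened decay curve is not supported either.

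Grade: should fix. It is a stated rule that conflicts with the stated aim, with a probably modest effect and a cheap remedy.

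**What to change.** Amend Participant Selection and the Invite procedure together:

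1. Keep every case with a positive PCR or positive serology before Visit 1 in the primary analysis set and the denominator, whatever the Visit 1 result.
2. Record a negative Visit 1 for these people as below detection. Count an earlier positive serology followed by a negative Visit 1 as loss of response between the two test dates.
3. Account for delayed entry at Visit 1 when estimating duration, or state that duration estimates are conditional on a response at Visit 1.
4. Limit the not-infected stop rule to cases with no prior laboratory evidence, and report them separately.

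The cost is wording and an analysis-set definition. Visit 1 results are already collected, so no extra visits are essential, although without them a later response in these people stays unobserved. The downside is that some prior positives will be false positives and would be counted as lost memory. A sensitivity analysis that excludes prior positives resting on a single unconfirmed test would show how much this matters.
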